2. Pregnant women and children (< 18 years as this is age of majority in NC) will also be excluded since the risks associated with hypertonic saline inhalation to the fetus or child and the risk of radiation are unknown and cannot be justified. Breastfeeding women will be excluded from this protocol.

3. Use of the following medications:

- a. Systemic corticosteroids; subjects with systemic corticosteroid-dependent asthma will be excluded. All use of systemic steroids in the last year will be reviewed by a study physician.
- b. Use of daily theophylline within the past month
- c. Use of beta blocking medications
- e. Receipt of LAIV (Live Attenuated Influenza Vaccine), also known as FluMist®, within the prior 30 days, or any vaccine within the prior 5 days
- f. Multivitamins, Vitamin C or E or herbal medications in the 4 days prior to the treatment visit
- g. Non-steroidal anti-inflammatory drugs in the 4 days prior to the treatment visit

4. Allergy/sensitivity to study drugs or their formulations:

[figure not shown]
Known IgE-mediated hypersensitivity to albuterol, diphenhydramine or corticosteroids.

5. Physical/laboratory indications:

- a. Abnormalities on lung auscultation
- b. Temperature > 37.8
- c. Systolic BP >150 mm hg or < 90 mm Hg or diastolic BP > 90 mm Hg or < 50
- d. Oxygen saturation of < 93%

6. Inability or unwillingness of a participant to give written informed consent.

4 STUDY PROCEDURES (See Appendix for Table of Study Procedures)

4.1 Visit 1 Baseline MCC: Subjects will be phone screened for potential eligibility. All subjects will be verbally screened for Covid 19 infection or exposure following current guidelines. The study, including risks and benefits, and what is expected of the subject will be explained and subjects will be given time to ask any questions. Once consent is obtained, a medical history, including all medications, will be collected. Subjects will be queried about any radiation exposure in the past year. A negative urine pregnancy test will be required of all women. Vitals signs, including

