4.9 Concomitant Medication documentation: Concomitant medications are collected at the screening visit and throughout the study visits. Subjects will use previously prescribed medication for their asthma. Subjects will not be asked to withhold any LABA/steroid combination medication on the morning of study visits. The study will provide all subjects with an albuterol MDI with spacer, and with 60 mg of prednisone as part of the asthma action plan at discharge. Subjects will be allowed to keep albuterol MDI with spacers for their personal use. Subjects will be asked to return unused prednisone tablets to the study staff during the follow-up visits.

4.10 Rescue medication administration: As with any testing in a population of subjects with asthma, albuterol (Ventolin® HFA) will always be available for rescue. There is also a code cart immediately available with epinephrine autoinjectors. Oxygen is available for supplementation if required.

4.11 Subject Completion/ Withdrawal procedures: Subjects are considered completed when the final 24-hour imaging, symptom questionnaire, vital signs and spirometry are collected. Subjects may withdraw at any time. Subjects will be asked to return to the lab for a final visit if they withdraw from the study prior to completion of all study procedures to monitor safety.

Subjects may be withdrawn at any time for safety concerns. Subjects who have any unanticipated problems (UPs) with the study procedures will be monitored until resolution of the symptoms.

Criteria for safety prior to HS inhalation:

(Subjects not meeting these criteria will not proceed with HS inhalation):

1. FEV₁ of at least 70% of predicted
2. FEV₁ within 10% of baseline value established at the screening visit.
2. Baseline oxygen saturation of at least 93%.
3. No history of viral respiratory tract symptoms within 4 weeks of challenge.
4. Vital signs within the previously defined normal parameters.
5. Symptom questionnaire score ≤ 2, , and no more than mild symptoms (ranked as “1”) reported for any category (see Section 5.3).

Criteria for safety of a given individual following HS inhalation which would suspend the individual from further participation in the study will include:

1. A 10% or greater decline in FEV₁ (from that day's baseline) at the 30-minute spirometry assessment.
2. *Continued* Symptoms of asthma exacerbation such as wheezing or respiratory distress.

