HS treatment will be deferred if baseline total symptom score > 2, OR any shortness of breath or fever are reported, OR if any symptom rated as moderate (2) or severe (3). For symptom scores obtained after HS treatment, subjects will be assessed by a study physician if total symptom score >2, if ANY shortness of breath is reported, or if any symptom is rated as moderate (2) or severe (3). If following HS treatment, the participant ranks any symptom as severe (3), that participant will be excluded from further study.

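### The pre-HS go/no-go list in Section 4.11 leaves out the deferral for any shortness of breath or fever that Section 5.3 applies, so the two symptom gates do not match

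*Combined protocol and SAP*

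**What the plan says.** Section 4.11 contains a list of safety criteria to be met before HS inhalation. Its heading gives the consequence of failing it: "Subjects not meeting these criteria will not proceed with HS inhalation". Item 5, the last in the list, asks for a questionnaire total of 2 or less and "no more than mild symptoms" (a rank of 1) in any category, and then refers to Section 5.3. Item 4 of the same list is "Vital signs within the previously defined normal parameters". The only temperature limit given earlier is the exclusion in Section 3.4, "Temperature > 37.8".

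Section 5.3 sets out the questionnaire: eight symptoms, each scored 0 to 3, with shortness of breath and fever among them. Its rule before treatment is: "HS treatment will be deferred if baseline total symptom score > 2, OR any shortness of breath or fever are reported". It adds deferral if any symptom is rated moderate or severe.

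Section 6.2 defines HS intolerance for the safety analysis. One of its components is a report of shortness of breath, with no grade attached and no comparison with the report before HS.

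**The concern.** Item 5 does not simply point to the rule in 5.3. It restates two of that rule's parts, the total score and the severity cap, and omits the third. Read on its own, it accepts a mild score in every category, including the two symptoms that 5.3 singles out. Nothing in the documents says which section governs if they differ.

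Two things are at stake. The first is who inhales HS on a given day, since 4.11 is the list that staff would naturally turn into a visit checklist. The second is the tolerability result. If a subject receives HS while already reporting mild shortness of breath and reports the same afterwards, the 6.2 definition counts that subject as intolerant although nothing has changed.

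**Working it through.** The plan gives no figure to reproduce here, so the check sets the two rules side by side.

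| Trigger before HS | 4.11 item 5 | 5.3 |
|---|---|---|
| Total score above 2 | stops HS | defers HS |
| Any symptom scored 2 or 3 | stops HS | defers HS |
| Any shortness of breath, including a score of 1 | not mentioned | defers HS |
| Any fever, including a score of 1 | not mentioned | defers HS |

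**Step 1: where the rules can differ.** If the total exceeds 2, or any item exceeds 1, both stop HS. They can therefore differ only when the total is 0 to 2 and every item is 0 or 1. Applying both rules to all 4^8 = 65,536 possible score patterns confirms this. Every disagreement is a pattern that item 5 passes and 5.3 defers, none runs the other way, and each one includes a mild score for shortness of breath or fever.

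**Step 2: mild shortness of breath alone.** The total is 1 and the maximum is 1, so item 5 is met and 5.3 defers. The other 4.11 items cover FEV1 against predicted, FEV1 against screening, oxygen saturation, recent viral respiratory symptoms and vital signs. None of them asks about shortness of breath. The synopsis requires not-well-controlled subjects to be free of wheezing and at their baseline before HS. That does not address shortness of breath either.

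**Step 3: mild fever alone.** Again the total is 1 and the maximum is 1, so item 5 is met and 5.3 defers. Here item 4 probably helps: if the parameters it refers to are those of Section 3.4, a measured temperature above 37.8 stops the subject. What remains is a self-reported mild fever with a temperature at or below that limit.

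**Step 4: link to the safety results.** Take a subject with mild shortness of breath before HS and the same afterwards.

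- Under 5.3 the subject does not receive HS that day.
- Under item 5 alone the subject does, and then meets the 6.2 definition of intolerance.
- Section 6.3 reports intolerance as a proportion of enrolled patients. With the planned 28, one such subject adds 1/28 = 3.6 percentage points.
- The study-level rule in 4.11 suspends the trial if 3 of the first 10 participants fail the individual criteria after HS. The relevant criterion joins any reported shortness of breath and any severe symptom with the word and. Read as alternatives, this subject counts as one of the three; read as a joint condition, the subject does not.

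**The case against.** The strongest reply is that the two sections do not contradict each other. The 4.11 list is worded as necessary conditions: failing an item bars HS, but nothing says that passing all of them is enough. Section 5.3 adds a further trigger, item 5 itself refers the reader there, and staff who follow the reference obey both. All of this stands, and it makes the point an incomplete restatement rather than a direct conflict. It does not remove the point, because a go/no-go list that restates part of a gate invites use without the rest.

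A reader might also draw stronger conclusions that the documents do not support:

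- *That the denominator of the intolerance proportion changes.* The synopsis and Section 6.3 define it on enrolled patients, which a symptom gate before HS does not alter. Only the numerator can move.
- *That subjects are lost before Visit 5.* Section 5.3 speaks of deferral, and Section 3.1 says subjects are rescheduled if their health status changes. No text turns a symptom deferral into withdrawal.
- *That the doubled comma in item 5 shows a dropped phrase.* The text was machine-read from PDF, and a stray comma is not evidence of what the sponsor meant to write.
- *That about 40% of subjects are affected.* Item 5 passes 1 + 8 + 28 = 37 score patterns and 5.3 passes 1 + 6 + 15 = 22, a difference of 15. These are combinations of answers, not patients, and they are not equally likely.

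**Conclusion.** The point holds as an omission in Section 4.11. Item 5 accepts mild shortness of breath, and mild self-reported fever without a temperature above 37.8, where 5.3 defers HS. The shortness-of-breath half is the firmer one, because no other 4.11 item covers it. The fever half is narrower and rests on the assumption that item 4 refers to the limits in Section 3.4.

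The size cannot be stated in subjects. The documents give no frequency for either symptom before HS, so the number affected among the 28 could be zero. The effect on the intolerance numerator assumes that staff work from 4.11 without following the reference, that the symptom is still reported after HS, and that the 6.2 definition supplies the numerator for the proportion in 6.3. The effect on the 3-of-10 rule also depends on how the post-HS criterion is read. The primary paired t-test and the sample size method do not depend on this point.

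**What to change.** Reconcile 4.11 item 5 and the pre-treatment rule in 5.3 into one symptom criterion, and print it in the same words in both places. Which rule applies is a clinical decision for the sponsor and investigator.

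Once it is settled, read Section 6.2 against it. If subjects with shortness of breath can receive HS under the agreed criterion, 6.2 should say whether a symptom already present before HS counts as intolerance. If they cannot, that question does not arise.

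The cost is a wording amendment and a matching update to any visit checklist. The endpoints, the sample size and the visit schedule need not change.

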6 STATISTICAL CONSIDERATION

6.1. Primary Endpoint:

change in MCC from baseline immediately after 7% HS inhalation

6.2 Secondary Endpoints

a. change in MCC from baseline immediately after albuterol inhalation. This endpoint is of exploratory interest.

b. Safety measures for HS treatment in moderate to severe asthmatics will include change in the following from baseline:

- Vital signs (HR, RR, BP and oxygen saturation)
- Spirometry (FEV1, FVC)
- Symptom Questionnaires
- Physical exam (wheezing on chest auscultation, for example)

We will also assess:

- Adverse events and Serious Adverse events
- Proportion of participants who are deemed 'intolerant' to HS (i.e. those who experience a persistent reduction in FEV1 of $\geq 10\%$ from that day's baseline at 30 minutes post-HS, those who report shortness of breath, those who report a score of "3" for any individual symptom criterion, or those who experience oxygen saturation levels below 90% for > 1 hour).

Safety endpoints will be assessed continuously during the study period for monitoring of adverse events and individual stopping criteria. All adverse events whether or not listed in the NCI-CTCAE (see Section 9) or whether they are or are not related to study participation will be graded on a scale from 1 to 5 according to the standards in the NCI-CTCAE manual. Adverse events will be reported to the UNC IRB, the UNC DSMB, and the NHLBI project officer. The DSMB will review the protocol after 5 subjects have completed study procedures or at 6 months after enrollment begins, whichever is soonest, and then every 6 months thereafter.

Exploratory endpoints will also be assessed. These will focus on sputum cellularity, mediators in sputum (e.g. T1 cytokines: IL-1 β , IL-6, IL-8, TNF α , T2 cytokines, IL-4, IL-5, IL-13), eicosanoids,

and mucins (total mucins, MUC5AC, MUC5B).

6.3 Statistical Methods

Our analytical plan was developed in collaboration with [name], the biostatistician for the CEMALB who will oversee all statistical analyses. The primary analysis of interest pertains to the difference between MCC measured at baseline and MCC measured during and after 7% HS challenge. The MCC measurements that define this difference are defined in section 5, and this difference has a unit of absolute percentage points. We will perform descriptive analysis of this difference; all point estimates will be tabulated along with their 95% confidence intervals. As we have assumed the sufficient underlying normality of MCC measurements, we will test the null hypothesis of no difference between baseline MCC and MCC immediately during and after 7% HS, against the alternative hypothesis of some difference, using a paired two-sided one-sample t-test with a 5% type I error rate. That is, if we let $\mu_{\Delta3\%}$ denote the mean difference between MCC measured at baseline and MCC measured during and immediately after the albuterol treatment, i.e. we will test the following hypothesis:

$$H_0: \mu_{\Delta\text{albuterol}}=0 \text{ vs. } H_1: \mu_{\Delta\text{albuterol}}\neq 0.$$

If the observed p-value is above 0.05, the test will be interpreted as being inconclusive. Following this test, we will perform sensitivity analyses to assess how realistic the assumption of normality was, and how much it may have impacted our conclusions. In particular, we will examine normal q-q plots and other descriptive tabulations, and we will examine the results of a Wilcoxon Signed Rank test. Should extreme or questionable observations arise in the study, we will also examine regression diagnostics to assess the influence of how those data were handled. The secondary analysis, which is of exploratory interest, pertains to the difference between MCC measured at baseline and MCC measured during and immediately after the 7% HS challenge. We will analyze this difference in a similar manner, i.e we will test the hypothesis

$$H_0: \mu_{\Delta7\%}=0 \text{ vs. } H_1: \mu_{\Delta7\%}\neq 0.$$

We will report the proportion of enrolled patients who do not tolerate HS at baseline, along with the 95% confidence interval of this proportion.

The effect of albuterol treatment on MCC will be assessed as a secondary endpoint, using the same techniques as described above for studies of 7% HS. We will also compare results following treatment with albuterol to those observed after 7% saline as an exploratory outcome. To do this analysis, we will assess the difference of the outcomes of these treatments within each individual and conduct appropriate paired t-tests. If these differences are not normally distributed, we will do proper transformation of the data to achieve a normal distribution. We will also conduct Wilcoxon signed rank tests in when data are not normally distributed.

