Study Rationale	Mucociliary clearance (MCC) is the process by which mucus is propelled from the lung toward the upper airway. Studies at our Center and others have demonstrated that hypertonic saline (HS) increases the volume of airway surface liquid, improves rheologic properties of mucus, and accelerates mucus transport rates in vitro . Inhaled 7% HS enhances MCC in healthy volunteers as well as those with muco-obstructive diseases like cystic fibrosis and chronic bronchitis. Improvements in MCC were also associated with improved lung function in CF. Use of HS as a treatment for asthma has been limited. Airway mucus plugging is a key feature of asthma and is responsible for much of the morbidity and mortality associated with the disease. We will explore the efficacy of albuterol alone and 7% HS with albuterol, compared to baseline for improving MCC in moderate to severe asthmatics.
Study Objective(s)	
Primary Objective
 
To determine the efficacy of HS for accelerating MCC acutely (immediately following HS) compared to baseline in well-controlled moderate to severe asthmatics.
 
Secondary Objectives
 
 - To compare the efficacy of albuterol alone vs 7% HS with albuterol pretreatment for accelerating MCC compared to baseline - To assess the safety of HS in moderate to severe asthmatics by measuring spirometry, vital signs, and symptom questionnaire scores. - Induced sputum samples after HS to assess for mucins and inflammatory endpoints
Test Article(s)	Sodium Chloride 7% solution for inhalation (Hereafter referred to as Hypertonic Saline or 7% HS) and albuterol for oral inhalation
Study Design	This is an open label proof-of-concept study. Participants will have a baseline MCC assessment, followed by sputum induction. They will return for another MCC assessment which will include treatment with 4 puffs of albuterol, and followed by a sputum induction. For the HS visit, in order to assess for acute effects of HS on MCC, subjects will be treated with 4 puffs of albuterol, and then will receive 7% HS inhalation immediately after start of the MCC measurement. Subjects will undergo sputum induction procedure after completion of MCC. All subjects will return the day following the HS visits for

medical assessment and to obtain lung images to approximate retention of radiolabeled particles at 24 hours.

Subject Population -	Inclusion Criteria

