	(4) Follow-up : Medical screening for safety endpoints, spirometry, and lung retention imaging will be performed the day following each treatment visit, and a discontinuation visit will be performed 5 to 10 days after the last study visit.
Efficacy Evaluations	To determine the efficacy of albuterol and HS with albuterol for acutely accelerating MCC in adult patients with moderate to severe asthma. We will prioritize comparison of acute effects of HS on MCC to baseline MCC measurements.

Pharmacokinetic Evaluations	None
Safety Evaluations	Vital signs, symptom questionnaire scores, spirometry
Statistical And Analytic Plan	
Primary Endpoint: difference between MCC measured at baseline and MCC measured with albuterol compared to MCC measured during and immediately after 7%HS inhalation, with MCC reported as the average percent retention of radiolabeled particles over 120 minutes of acquiring images. We will perform descriptive analysis of this difference; all point estimates will be tabulated along with their 95% confidence intervals. As we have assumed normality of MCC measurements, we will test the null hypothesis of no difference between baseline MCC and MCC immediately post-HS, against the alternative hypothesis of some difference, using a paired two-sided one-sample t-test with a 5% type I error rate. If the observed p-value is above 0.05, the test will be interpreted as being inconclusive. Following this test, we will perform sensitivity analyses to assess how realistic the assumption of normality was, and how much it may have impacted our conclusions. In particular, we will examine normal q-q plots and other descriptive tabulations, and we will examine the results of a Wilcoxon Signed Rank test. Should extreme or questionable observations arise in the study, we will also examine regression diagnostics to assess the influence of how those data were handled.
 
Secondary Endpoints: difference between albuterol and 7% HS effect on MCC and mucins/neutrophils in induced sputum post treatment. Finally, we will report the proportion of enrolled patients who do not tolerate HS at baseline, along with the 95% confidence interval of this proportion.

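### Section 6.3 gives the primary 5% test to 7% HS in words, writes the formal hypothesis for albuterol, and then calls the 7% HS comparison secondary

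*Combined protocol and SAP*

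**What the plan says.** Section 6.3 makes four statements in this order.

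1. It opens with the primary comparison: "The primary analysis of interest pertains to the difference between MCC measured at baseline and MCC measured during and after 7% HS challenge". The test follows in words: "we will test the null hypothesis of no difference between baseline MCC and MCC immediately during and after 7% HS", by a two-sided paired t-test at 5%.
2. A sentence beginning 'That is' should restate this test formally. It introduces a mean difference with the subscript 3%, defines it as baseline against "MCC measured during and immediately after the albuterol treatment, i.e. we will test the following hypothesis", and displays H0: μ_Δalbuterol = 0 against a two-sided alternative.
3. The decision rule comes straight after that display: "If the observed p-value is above 0.05, the test will be interpreted as being inconclusive". The normality checks and the Wilcoxon test are then tied to this test.
4. The next analysis is introduced with "The secondary analysis, which is of exploratory interest, pertains to the difference between MCC measured at baseline", and the measurement set against baseline is the one with 7% HS. Its hypothesis is displayed as H0: μ_Δ7% = 0.

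The last paragraph of the same section turns the order round again: "The effect of albuterol treatment on MCC will be assessed as a secondary endpoint".

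Elsewhere, the synopsis gives the primary objective as "To determine the efficacy of HS for accelerating MCC acutely (immediately following HS) compared to baseline" and says under Efficacy Evaluations: "We will prioritize comparison of acute effects of HS on MCC to baseline MCC measurements".

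**The concern.** One section calls the same contrast both primary and secondary/exploratory. The displayed hypothesis is the formal statement of the primary test, and it names the wrong treatment. This is more than one mistyped symbol: the parameter definition, the displayed H0 and H1, and the later sentence on the secondary analysis all carry the reversed order. The subscript 3% fits neither its own definition nor the hypothesis displayed under it.

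At stake is which result the study reports as its primary finding. An analyst who follows the displayed hypothesis would report albuterol versus baseline as the 5% test and 7% HS versus baseline as exploratory. No objective or endpoint section supports that reading. The study is open label and section 6.5 plans interim efficacy analyses of 7% HS, so results may be seen before the text is corrected. The primary contrast should be settled in writing before then.

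**Working it through.** **Step 1. The statements side by side**

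| Place | 7% HS vs baseline | Albuterol vs baseline |
|---|---|---|
| Synopsis, primary objective; section 2.1 | primary | not named |
| Synopsis, Efficacy Evaluations | given priority | also listed |
| Synopsis, test sentence in the statistical plan | 5% paired test | no test stated |
| 6.1 | primary | not named |
| 6.2a | not named | secondary, exploratory |
| 6.3, opening prose | primary, 5% paired test | not named |
| **6.3, formal hypothesis** | **not named** | **takes the place of the primary test** |
| **6.3, sentence after the sensitivity analyses** | **secondary, exploratory** | **not named** |
| 6.3, last paragraph | source of the methods | secondary |
| 6.4 | primary, used for sizing | not named |

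The two rows in bold disagree with the rest. Section 2.2 is weak evidence, because it sets albuterol against HS, not against baseline. Section 6.5 plans its interim efficacy analyses for 7% HS, which shows what will be looked at but not by itself what is primary.

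**Step 2. Which contrast the sample size belongs to**

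Inputs from section 6.4: difference 7 points, SD of the difference 10 points, two-sided α = 0.05, and 0.9 (printed as β, read here as power).

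n = [SD × (z₀.₉₇₅ + z₀.₉₀) / δ]² = [10 × (1.960 + 1.282) / 7]² = 21.44

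The plan states 21. Rounded up, the formula gives 22, so the stated figure is reproduced to within one patient. Inflation: 21 × 1.3 = 27.3, rounded up to 28, as stated. Section 6.4 attaches this calculation to baseline versus HS. Correcting the hypothesis in 6.3 leaves it as it is. (An exact paired t calculation needs 24; that is a separate matter.)

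**Step 3. What the two readings change**

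Both contrasts get the same paired test and confidence interval, because 6.3 says the second is analysed like the first. The HS estimate, interval and p-value are therefore identical under either reading. Only the label changes.

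**Step 4. An illustration, not a property of the plan**

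Suppose the primary contrast were chosen after both results were known and neither treatment worked. With independent tests the chance of at least one p < 0.05 is 1 − 0.95² = 0.0975. For one final analysis of 21 pairs, simulation with 1,000,000 trials per setting gave 9.7%, 9.1%, 7.9% and 7.1% at correlations of 0, 0.5, 0.8 and 0.9 between the two differences. The documents give no correlation, so these values are assumptions. Nothing in the plan says the choice would be made this way.

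**The case against.** The strongest reply is that nobody would be misled. The synopsis states the whole test correctly for HS: paired, two-sided, 5%, with the same rule for a p-value above 0.05 and the same normality checks. Section 6.3 largely corrects itself too, because its last paragraph refers back to the methods above as those for 7% HS. Sections 6.1, 6.2a and 6.4 fix the order, and no computed result changes. On this view it is a drafting slip in a proof-of-concept study.

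Most of this stands. The intent is recoverable, the numerical results are the same, and the error rates in step 4 should not be read as alpha inflation in the plan. What does not follow is that the text can be left alone. The formal hypothesis and the secondary label sit in the section an analyst works from, and both say the opposite of the intent. The synopsis is not a clean reference either: its primary endpoint sentence also brings in the albuterol measurement, so a reader who checks there meets a second ambiguity.

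**Conclusion.** The concern holds. Section 6.3 is wrong as written and should be fixed. Its formal hypothesis and its sentence on the secondary analysis reverse the order that its own opening and the rest of the plan set out. The effect is on which result is primary. Alpha, the 21 evaluable and 28 recruited, and the HS estimate, interval and p-value are unaffected.

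The conclusion rests on the text alone and needs no assumed figure. That the 3% subscript is left over from an incomplete edit is likely, since section 5.1 still mentions a 3% versus 7% HS comparison, but this is an inference. Correcting 6.3 does not by itself secure a 5% error rate, because section 6.5 plans interim efficacy analyses of 7% HS with no stated alpha adjustment. That is a separate matter and is not counted here.

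**What to change.** In section 6.3:

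- Define μ_Δ7% as the mean within-subject difference in MCC between baseline and 7% HS, and state H0: μ_Δ7% = 0 against H1: μ_Δ7% ≠ 0 as the only primary test at two-sided 5%.
- Put the 0.05 rule and the sensitivity analyses directly after that hypothesis.
- Move H0: μ_Δalbuterol = 0 to the secondary/exploratory paragraph, in line with 6.2a and the last paragraph of 6.3.
- Delete the 3% subscript and the sentence calling the 7% HS comparison secondary.

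Two smaller consistency edits belong with this. The synopsis primary endpoint, which now mixes three measurements, should name baseline versus 7% HS. Section 5.1 should be reconciled with the treatments in the current design, which has no 3% HS treatment visit.

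The cost is a wording amendment to the protocol and SAP, made before any efficacy analysis, interim ones included. Alpha, sample size, visits, data and patients are not affected.
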